If the sensed glucose is ≥ 300 mg/dl, the participant will be instructed to check their blood glucose and to check the Omnipod for malfunction. This would include checking for insulin leaks, making sure Omnipod is securely adhered to skin, and check for error messages on the phone running the algorithm.

If capillary blood glucose value is over 300 mg/dl for more than 2 hours or is ≥ 400 mg/dl at any time, the participant will be instructed to check serum ketones using the Abbott Precision Xtra meter and to change out the Omnipod. If serum ketones are over 0.6 mM, the participant will be instructed to contact the study investigator to discuss proper management, including delivering a correction bolus. (see Appendix C 'Safety Instructions for Participants' for instructions provided to participants on when to contact study staff) In addition, the participant will be encouraged to drink sugar-free liquids. If serum ketones are above 1.5 mM at any time, the study will be stopped and insulin will be administered as directed by the on call investigator.

Cleaning and Disinfecting

All devices will be cleaned and disinfected between participants. The smart phone, Dexcom G6 transmitter, heart rate monitor and Omnipod PDMs are cleaned by study staff. Technicians who are disinfecting units will wash hands thoroughly and wear gloves. All items will undergo intermediate-level disinfection using Oxivir TB disposable wipes. The disinfectant will be applied and allowed to air dry. After disinfection, when the units are completely dry, they will be placed in a sealed bag labeled with participant information.

Stopping Rules

Individual study stopping rules

The closed-loop study will be stopped and the participant's own pump will be resumed under the guidance of the on call study investigator if any of the following occur after the start of the study:

the participant requests that the treatment be stopped, participant pregnancy, one episode of diabetic ketoacidosis as defined as symptoms such as polyuria, polydipsia, nausea, or vomiting, serum ketones >1.5 mmol/L or moderate/large urine ketones, either arterial blood pH <7.3 or venous pH <7.24 or serum bicarbonate <15 , and treatment provided in a health care facility, or one episode of severe hypoglycemia defined as a hypoglycemic event resulting in altered consciousness requiring another person to actively administer carbohydrate, glucagon, or other resuscitative actions.

Entire study stopping rules

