26	maximum_insulin_exceeded: Insulin Delivery \geq 35% TDIR _{adj} on last hour	User acknowledgement		"Max insulin has been exceeded"	-	60	Immediately	Immediately	-
27	cbg_equal_or_over_400: CBG \geq 400 mg/dl AND alert 27 not active or refractory	Ketone check		"Blood glucose is above 400 mg/dl. Please change the insulin pod and check ketone levels now."	15 min	60	Immediately	Immediately	-
28	ketone_level_high: Ketones \geq 0.6 mmol/L	User acknowledgement		"Ketone levels are high. If not already done, please change the insulin pod. Do not exercise."	-	-	Immediately	Immediately	-
29	Insulin pump reservoir_low: Omnipod	Pod with greater than 10% volume is		Your insulin pod is low. Please	120 min	-	After 1st re-fire	After 2nd re-fire	-

	has less than 10% of fluid volume remaining.	connected (i.e. pod is changed)		deactivate your current pod and activate a new insulin pod.					
30	External_insulin_detected_alert: iPancreas has determined that more insulin has been delivered than expected by observing the insulin pump' pulse count	None, this alert only goes to the study coordinator and investigator.	The app determined by the pump's pulse count that more insulin than was expected was delivered.	We determined that X.X units of insulin above the expected amount was delivered. Please switch to open loop mode and call study team.	-	-	Immediately	Immediately	-
31	Sensor_glucose_extremely_low: This alert fires when CGM is measured to be <= 54 mg/dL.	Measured CGM > 54 mg/dL.	This alert fires if CGM is measured to be < 54 mg/dL. When this alert is active, the sensor_glucose_low is suppressed. If CGM goes from <= 54 to between 70-54 mg/dL, the sensor_glucose_low alert will fire again after the refractory period of 30 minutes expires	"Sensor value is extremely low" "Sensor glucose is below 54 mg/dL. Please perform a blood glucose check now."	10 min	30	After first re-fire	After second re-fire	-

			on the recently cleared sensor_glucose_extremely_low alert						
32	extreme_hypoglycemia_predicted: fires when CGM is predicted to be ≤ 54 mg/dL within the next 30 minutes.	CGM is no longer predicted to be ≤ 54 mg/dL within the next 30 minutes, or CGM is measured to be ≤ 54 mg/dL.	This alert fires if the LSTM predicts that the CGM will drop < 54 mg/dL.	Your blood glucose is predicted to drop below 54 mg/dl within 30 minutes. Please consider taking a rescue carbohydrate.	15 min	30	After first re-fire	After second re-fire	-

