43	re_pair_pdm: The app detects an issue with the Bluetooth connection to the PDM.	User acknowledgement		Your PDM seems to be having trouble communicating and needs to be un-paired / re-paired. Please disconnect the device from iPancreas. Then go to the Android Bluetooth menu, forget the device, then re-pair it.	-	-	-	-	
44	insulin_pod_empty: The app detects the pod is empty.			Your insulin pod is empty. Please replace it immediately.	30 minutes	none	never	never	
45	insulin_pod_expires_soon: the app detects that it has been 71 hours since pod was started.			Your insulin pod will expire soon. Please replace it immediately.	60 minutes	none	never	never	

Appendix C: Safety instruction cards for participants for checking ketones, to take additional carbs at the start of exercise as needed based on CGM and trend to avoid post-exercise hypoglycemia, for study stopping rules.

Instruction cards:

Sensor glucose during exercise at home	G6 Trend arrow direction	Action
Ketones above 0.6 mmol/L	all	Stop/do not start exercise. Contact study staff.
Greater than 270 mg/dl with ketones less than 0.6 mmol/L	all	Proceed with exercise.
145-270 mg/dl	all	Proceed with exercise.
Less than 145 mg/dl	↑ or ↗	Proceed with exercise.
	→	Consume 15 grams carbs. Proceed with exercise.
	↘	Consume 25 grams carbs. Proceed with exercise.
	↓	Consume 35 grams carbs. Proceed with exercise.
Less than 100 mg/dl	all	Do not start exercise. Check fingerstick glucose. Consume 15 grams of carbs every 15 minutes until fingerstick glucose is above 100 mg/dl.

iPancreas Study instructions for when to stop your study for safety

Please stop your study in iPancreas, resume your own pump and contact your study team if any of the following occur:

1. Pregnancy
2. You were diagnosed and treated in a health care facility for Diabetic ketoacidosis.
3. One episode of severe low blood sugar where you required another person to give you glucagon, carbohydrates or other treatment actions.

<insert site study team contact information>

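### The stop on serum ketones above 1.5 mM and the call above 0.6 mM stand in the hyperglycemia guideline but are not carried into the individual stopping list, alert 28 or the participant's stop card

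*Protocol*

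**What the plan says.** Four places in the protocol bear on ketones and stopping (mM and mmol/L are the same unit).

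- **Hyperglycemia Treatment Guidelines.** There are two tiers. Lower tier: "If serum ketones are over 0.6 mM, the participant will be instructed to contact the study investigator to discuss proper management". Here the text points to the Appendix C card "for instructions provided to participants on when to contact study staff". Upper tier: "If serum ketones are above 1.5 mM at any time, the study will be stopped", with insulin then directed by the on-call investigator.
- **Individual study stopping rules.** This part opens with the action: "The closed-loop study will be stopped and the participant's own pump will be resumed under the guidance of the on call study investigator". It applies on any of four triggers: participant request, pregnancy, DKA or severe hypoglycemia. Ketones enter only through DKA, where a serum value above 1.5 mmol/L (or a urine equivalent) must be joined to symptoms, to a pH or bicarbonate criterion and to treatment in a facility.
- **Appendix B, alert 28.** It fires at ketones of 0.6 mmol/L or more. Its message begins "Ketone levels are high. If not already done, please change the insulin pod" and adds only that the participant should not exercise. It clears when the user acknowledges it, and no re-fire time is listed.
- **Appendix C, stop card.** It has three triggers: pregnancy, severe low blood sugar and, for ketosis, "You were diagnosed and treated in a health care facility for Diabetic ketoacidosis". It gives no ketone value.

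The only line in Appendix C where a ketone value prompts contact with staff is on the exercise card (above 0.6 mmol/L).

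**The concern.** The guideline lets a ketone reading alone end closed-loop use. The other three places do not repeat that condition. The one ketosis-related event on the stop card, facility-treated DKA, can be recognised only after the participant has already been treated. The guideline's sentence is therefore the only ketone stop that can operate while the participant is still at home on the study system.

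Home ketone readings are planned for. The guideline asks for them when capillary glucose stays over 300 mg/dl for more than 2 hours or reaches 400 mg/dl, and alerts 7 and 27 clear on a ketone check. At that moment the participant has the alert text and the cards in hand. If these omit the guideline's two conditions, the conditions depend on what the participant remembers from training or on a call that neither the alert nor the stop card asks for. The stake is participant safety and uniform conduct across two sites.

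**Working it through.** The protocol states no figure to reproduce and no arithmetic applies. The check sets the places side by side and runs two ketone values through them.

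| Place | Ketone value alone stops the study? | Asks for contact on a ketone value? |
|---|---|---|
| Hyperglycemia Treatment Guidelines | Yes, above 1.5 mM | Yes, above 0.6 mM |
| Individual study stopping rules | No; above 1.5 mmol/L only within DKA | No |
| Appendix B, alert 28 | No; one message from 0.6 mmol/L upward | No |
| Appendix C, stop card | No ketone value given | No; contact only with one of its three triggers |
| Appendix C, exercise card | No; it concerns exercise | Yes, above 0.6 mmol/L, during or before exercise |

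**Case A: ketones 2.0 mM at home, no acidosis shown, no facility treatment.**
- Guideline: 2.0 > 1.5, so the study stops. Also 2.0 > 0.6, so the participant should be in contact with the investigator.
- Individual stopping rules: the ketone component is met, but the acidosis and facility-treatment components are not. No trigger is met.
- Withdrawal Criteria: DKA is defined the same way there, so that criterion is not met. The general clauses on danger to health and investigator discretion remain available.
- Alert 28: 2.0 ≥ 0.6, so it fires. The participant is told to change the pod and not to exercise.
- Stop card: no trigger is met.

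**Case B: ketones 0.9 mM, not exercising.**
- Guideline: 0.9 > 0.6, so contact the investigator.
- Alert 28: the same message as in Case A, with no request to call.
- Stop card: no trigger is met.

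Alert 28 therefore does not distinguish Case A from Case B, although the guideline treats them differently. Other alerts in the same table do ask for contact: alert 30 tells the participant to call the study team, and alert 40 to contact the coordinator. Leaving contact out of alert 28 is thus not a convention of the table.

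**Staff backstop.** Appendix B pushes alert 28 to the coordinator and investigator immediately, but both push columns are limited to remote monitoring. Under Safety assessment – first 5 participants, remote monitoring may be removed after five participants complete both arms, if the safety criteria are met. From then on the push would not apply.

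**Scope of the 1.5 mM sentence.** It says only that the study will be stopped. The Entire study stopping rules halt everything for severe hypoglycemia or DKA, and stop studies for unexpected events such as death or hospitalization. A ketone value alone is not among them. Context suggests the individual's closed-loop study is meant, but the sentence does not say so.

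**The case against.** The strongest case against the point is that these texts do not conflict. The individual list stops closed-loop use "under the guidance of the on call study investigator if any of the following occur after the start of the study". It does not say only if, so the guideline adds a fifth trigger and an investigator can follow both. The protocol also routes the decision through the investigator: anyone above 1.5 mM is already above 0.6 mM and, under the guideline, should already be calling. An investigator is available in person or by phone for all 7 days. Participants are trained on the action each alert requires, so the alert text need not be the whole instruction. A coordinator remains able to view the system remotely. Finally, the Appendix C heading mentions cards for checking ketones, and a further card may not have been reproduced in the text at hand.

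Much of this stands, and it rules out some stronger readings.

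- A reader might infer that participants with the same ketone value would be stopped or continued depending on the page consulted. That treats silence as an instruction. No text says to continue above 1.5 mM.
- A reader might say the 1.5 figure is absent from the stopping list. It is there, inside DKA; only the stand-alone trigger is absent.
- A reader might take 28 − 5 = 23 intervention weeks as affected. That counts weeks possibly without staff push, and only if the safety review allows it. It does not count weeks with ketones above 1.5 mM, for which the documents give no frequency.

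The objection does not remove the gap. Training and the contact tier work only if the participant calls, and the alert and stop card shown do not ask for that on a ketone value. The guideline itself sends the reader to Appendix C for when to contact staff, and outside exercise no ketone value there prompts it.

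**Conclusion.** The point holds as an incomplete carry-over of a safety condition, not as two opposed rules. One of the four places contains the stand-alone stop above 1.5 mM. Neither the stop card nor alert 28 contains the call above 0.6 mM. The count describes the documents and is not an effect size.

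A reader might also infer a loss of intervention-period data. The documents do not support a size for that. A visit stopped early may be repeated, a period counts with at least 24 hours of data, and sample size, power and type I error are untouched.

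The conclusion assumes that the Appendix C cards shown are the complete set given to participants. It also takes the push columns at their word as applying only under remote monitoring. The mitigations lower the risk, but the correction is cheap and safety-relevant, so it should be made. No view is taken on which stopping rule is right.

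**What to change.** The clinical team must reconcile the Hyperglycemia Treatment Guidelines, the Individual study stopping rules, alert 28 and the Appendix C stop card so that all four carry the same ketone condition and the same action, whichever the team decides on. The team should also state whether the study in the 1.5 mM sentence means the individual's closed-loop study or the entire trial. If a separate ketone card exists, Appendix C should show it.

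The cost is a protocol wording change, one reprinted card and possibly one alert text in the app. Design, sample size and analysis do not change.

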If at any time study staff determines that a sensor can no longer be used, a new sensor will be inserted. In order to ensure safety and to assess sensor accuracy, the participant will be asked to check their capillary blood glucose before and after exercise (if the participants selects to exercise), for symptoms of hypoglycemia, and in response to system alert (such as for low or high sensor alerts).

For participant safety, if a sensor value is not available for 20 minutes or communication with the Omnipod is lost for more than 30 minutes, the Omnipod will begin insulin delivery according to a pre-set basal profile(s) inputted for the participant at study start. When this occurs for a lost sensor, iPancreas will activate the predictive low glucose suspend feature if the last known sensor value was within the range of 70-140 mg/dl and predicted to fall below 90 mg/dl within

thirty minutes or if the sensor glucose is less than 70 mg/dl. Insulin is suspended for 30 minutes, after which basal insulin delivery resumes. When communication with the sensor or Omnipod is restored, the system will automatically resume, updating the IOB accordingly.

The food items will be self-selected by the participant.

Safety assessment – first 5 participants

We are proposing to remove remote monitoring after the successful completion of the first 5 participants if the safety criteria are satisfied. We will complete an interim analysis after the first 5 participants complete both arms of the study assessing time spent with CGM < 54 mg/dL, <70 mg/dL, and > 300 mg/dL and any adverse events. The closed-loop system data will be compared to the equivalent data from the participant's 7-Day Control period with the use of their personal closed loop system, either the t:slim X2 with Control IQ or Omnipod 5 system. If the interim analysis shows that the closed-loop system data is comparable to usual care studies and presents no safety concerns, we will proceed to enrolling participants without remote monitoring. If it does not or if there are any instances of severe hypoglycemia or DKA (unrelated to infusion set failure), then the study will be halted, changes will be made as appropriate to algorithm and the protocol and a plan will be submitted to FDA and IRB that will need to be approved before further studies are conducted. After the algorithm adjustments are made, an additional 5 participants will then be completed with remote monitoring.

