Severe hypoglycemia is defined as any event that required the assistance of another person to administer carbohydrate, glucagon, or other resuscitative actions. Diabetic ketoacidosis is classified as: symptoms such as polyuria, polydipsia, nausea, or vomiting, serum ketones >1.5 mmol/L or moderate/large urine ketones, either arterial blood pH<7.3 or venous pH<7.24 or serum bicarbonate <15, and treatment provided in a health care facility. If an event of severe hypoglycemia or diabetic ketoacidosis should occur, the study will be halted and a description of the serious adverse event and a new risk mitigation plan will be submitted to the FDA. The study will only resume once FDA approval is received.

We are aware that there is a risk of severe hypoglycemia while the participants are at home. The system will alert if the sensed glucose values fall below 70 mg/dl prompting the participant to obtain a capillary blood glucose sample. Participants will be required to live with at least one other person age 18 or older and live within 40 miles of the study site that enrolled the participant.

In case of a system error that cannot be corrected immediately with the participant off campus, the participant will be able to go into open-loop mode. This will allow the Omnipod to begin basal insulin delivery for a pre-set basal profile(s) inputted for the participant at the study start. Participants will be able to give meal boluses and corrections through the Omnipod while in open-loop mode. When the error is resolved, the participant can resume closed-loop mode and the system will resume. If the participant goes into open-loop mode, this will be visible on the cloud server and may prompt a telephone call from study staff to determine the issue and the best way to resolve it. The participant may contact study staff at any time during the outpatient portion of the visit.

Discharge from inpatient clinic

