Triggers for reporting unanticipated problems are seizure, hospitalization, death or any other occurrence considered serious by the PI and Medical Monitor. If any studies are stopped for severe hypoglycemia or diabetic ketoacidosis, then the entire study will be halted. Severe hypoglycemia is defined as any event that required the assistance of another person to administer carbohydrate, glucagon, or other resuscitative actions. Diabetic ketoacidosis is classified as: symptoms such as polyuria, polydipsia, nausea, or vomiting, serum ketones >1.5 mmol/L or moderate/large urine ketones, either arterial blood pH <7.3 or venous pH <7.24 or serum bicarbonate <15 , and treatment provided in a health care facility. If an event of severe hypoglycemia or diabetic ketoacidosis should occur, the study will be halted and a description of the serious adverse event and a new risk mitigation plan will be submitted to the FDA. The study will only resume once FDA approval is received. In addition, if there is any unexpected event such as death or patient hospitalization, the studies will be stopped until the root cause is evaluated.

The Model Predictive Control (MPC) Algorithm

Our MPC algorithm uses a glucoregulatory model to predict glucose outcomes over a predicted horizon and mathematically solve for the optimal insulin doses across the control horizon to bring the participant to target. The model is updated at each timestep by a Kalman filter, which uses the difference between CGM observations and model predictions to update the physiologic model states. In short, a model-predictive controller uses a physiologic model to calculate how much insulin is required to bring someone to glucose target, and these predictions are adapted to the specific participant using a Kalman filter.

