- Requires medical or surgical intervention to prevent permanent impairment or damage

Exceptions to the SAE definition will include the following:

- Elective surgery
- A planned hospitalization for pre-existing condition, without a serious deterioration in health

Any SAE, including death, due to any cause (related or unrelated to the device), that may occur during a clinical study will be reported to the PI and Medical Monitor immediately (within 1 working day of learning of the event).

Severity of Adverse Events

The following definitions may be used to rate severity of AEs:

- **Mild**

Awareness of signs or symptoms, but easily tolerated; are of minor irritant type that is outside the norm for the disease state or subject; causing no loss of time from normal activities; symptoms would not require medication or a medical evaluation; signs and symptoms are transient. Mild hypoglycemia is expected in diabetes and will not be captured as an AE.

***Example:** ketosis not requiring an ER visit.*

- **Moderate**

Discomfort severe enough to cause interference with usual activities, requiring treatment by family member or emergency personnel

Example: infusion site infection requiring antibiotics prescribed at urgent care.

- **Severe**

Incapacitating, causing inability to do work or usual activities; signs and symptoms may be of systemic nature or require medical evaluation and/or treatment at a health care facility

Example: severe hypoglycemia defined as hypoglycemic event resulting in altered consciousness requiring another person to actively administer carbohydrate, glucagon, or other resuscitative actions.

Relationship of Adverse Events to Study or Study Device

The investigator will categorize the relationship of the event to the study or study device as follows:

- **Not Related**

AE is due to an underlying disease state or concomitant medication or therapy not related to the device, disease or study.

- **Unlikely Related**

AE has minimum or no temporal relationship to the study device, disease or study participation and/or a more likely alternative etiology exists.

- **Possibly Related**

AE has a strong temporal relationship to the study device, disease or study procedures and alternative etiology is equally or less likely compared to the potential relationship to the device, disease or study.

- **Probably Related**

AE has a strong temporal relationship to the study device, disease or study and another etiology is unlikely.

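### The home exercise card gives opposite instructions below 100 mg/dL, and the severe hypoglycemia definition and the early DKA halt rule each stand in two inconsistent forms

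*Protocol*

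**What the plan says.** **Exercise card (Protocol, Appendix C).** Participants receive the card in both study periods, for use if they choose to exercise. For sensor glucose below 145 mg/dL it has four rows by trend arrow. Rising arrows may go ahead. The flat arrow reads "Consume 15 grams carbs. Proceed with exercise". The two falling arrows call for 25 g and 35 g of carbohydrate and then also go ahead. A separate row for readings below 100 mg/dL, all arrows, says "Do not start exercise. Check fingerstick glucose", followed by 15 g of carbohydrate at 15-minute intervals until the fingerstick value is above 100 mg/dL.

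**Severe hypoglycemia.** Individual study stopping rules end closed loop after "one episode of severe hypoglycemia defined as a hypoglycemic event resulting in altered consciousness requiring another person to actively administer carbohydrate". The section Severity of Adverse Events gives, as its example of the highest grade, "severe hypoglycemia defined as hypoglycemic event resulting in altered consciousness requiring another person to actively administer carbohydrate, glucagon, or other resuscitative actions". A wider definition stands in Withdrawal Criteria, in the safety assessment of the first 5 participants and in Entire study stopping rules: "Severe hypoglycemia is defined as any event that required the assistance of another person to administer carbohydrate, glucagon, or other resuscitative actions". The participants' own stop list in Appendix C is also wide: "One episode of severe low blood sugar where you required another person to give you glucagon, carbohydrates or other treatment actions".

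**Diabetic ketoacidosis (DKA).** In the safety assessment of the first 5 participants, the interim decision says "if there are any instances of severe hypoglycemia or DKA (unrelated to infusion set failure), then the study will be halted". Later in that section, and again in Entire study stopping rules, the sentence has no exception: "If an event of severe hypoglycemia or diabetic ketoacidosis should occur, the study will be halted".

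**The concern.** These passages decide whether a participant exercises at a low glucose reading, whether closed loop is stopped, and whether the trial halts. Each should give one answer for one reading or one event.

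The card matters most. It is read by participants at home, without staff beside them, and remote monitoring may be dropped after the first five participants. A participant who follows the first row that fits the reading, and one who follows the last row that fits, would do opposite things.

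The other two items are read by staff and investigators at two sites. Two people who each follow the protocol could classify the same assisted low, or the same DKA after an infusion set failure, differently.

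**Working it through.** No sample size, power or error rate is involved, so the check is to apply each version of a rule to the same case and compare the results.

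**Reading: sensor glucose 95 mg/dL.** 95 < 145 is true, and so is 95 < 100. Both blocks of the card apply.

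| Arrow | Rows below 145 mg/dL | Row below 100 mg/dL |
|---|---|---|
| Rising | go ahead | do not begin |
| Flat | 15 g, go ahead | do not begin |
| Slanting down | 25 g, go ahead | do not begin |
| Straight down | 35 g, go ahead | do not begin |

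The value 95 is only an example. Any x < 100 also satisfies x < 145, so the overlap is the whole band below 100 mg/dL, for every arrow listed. The carbohydrate instruction differs as well: one fixed amount or none in the first block, repeated 15 g with fingerstick checks in the second. The card has no sentence saying which row takes precedence.

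**Event: another person has to treat the low, consciousness is unaltered.**

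| Place | Altered consciousness needed? | Result |
|---|---|---|
| Withdrawal Criteria | no | participant must be withdrawn |
| Safety assessment, first 5 | no | study halted |
| Entire study stopping rules | no | study halted |
| Appendix C stop list | no | participant stops and resumes own pump |
| Individual study stopping rules | yes | criterion not met |
| Severity of Adverse Events, example of Severe | yes | example does not fit |

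Four places use the wider definition and two the narrower. The same event leads to withdrawal and a trial halt, yet falls outside the rule for stopping that participant's closed-loop study. Its grade is also left open: the Moderate category mentions treatment by a family member, and the Severe example does not describe the event.

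**Event: DKA related to infusion set failure, among the first five participants.**

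| Place | Exception? | Result |
|---|---|---|
| Safety assessment, interim decision | yes | this sentence does not call for a halt |
| Safety assessment, later sentence | no | study halted |
| Entire study stopping rules | no | study halted |

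One sentence excepts the event and two do not; one of the two is in the same section.

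**The case against.** On the card, the row below 100 mg/dL has a purpose only if it overrides the rows above it, so the conflict may be no more than a missing lower limit. That is a fair guess at the drafting, but the card does not say it, and a lay instruction used at home should not depend on that inference.

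On severe hypoglycemia, a reader might infer that the narrower rule tells staff to keep closed loop running, or leaves the trial halt in doubt. The protocol supports neither. Failing to meet one stopping criterion is not an order to continue, and the withdrawal criterion and the participants' stop list still apply. Entire study stopping rules carry their own wide definition and a trigger that does not wait for an individual stop. A reader might also infer that counts of serious adverse events would change. The Serious Adverse Events section tests for death, threat to life, hospitalization, disability or intervention to prevent permanent harm, and neither definition enters that test. The severity definitions are themselves optional. What stands is a duplicate definition that does not match.

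On DKA, the exception belongs to the interim decision about ending remote monitoring, which has its own consequences (changes to algorithm and protocol, then five more monitored participants). It never says that the study continues after an excepted event, and the unqualified sentences would still halt it. A reader might take the conflict as trial-wide, or take the exception to cover pod failures. The documents limit it to the first-five assessment and do not equate a pod with an infusion set. What stands is that the exception and the unqualified sentence govern the same halt in the same section, with nothing to say how they fit together.

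**Conclusion.** The three inconsistencies are in the current text and are of unequal weight.

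- **Exercise card:** a direct contradiction covering every reading below 100 mg/dL and every listed arrow. It needs correction before the card is used. This assumes only that the row labels in Appendix C are complete as printed.
- **Severe hypoglycemia:** two definitions over six places, four wide and two narrow. The effect is limited to the individual stopping rule and the severity example; withdrawal and the study halt follow from the wide definition.
- **DKA:** one halt sentence with an exception against two without, limited to the safety assessment of the first five participants.

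None of this is shown to affect the primary endpoint, the power or the analysis. Which clinical rule is right is for the clinical team and is not judged here.

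**What to change.** Reconcile the passages in one amendment.

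1. Make the glucose bands on the exercise card mutually exclusive, or state on the card which row governs when two apply.
2. Define severe hypoglycemia once and refer to that definition in Withdrawal Criteria, the safety assessment, both sets of stopping rules, the severity example and the participants' stop list.
3. State in one place whether the infusion-set exception applies to the DKA halt during the first-five assessment, and have the other sentences refer to it.

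The clinical team chooses the content of each rule. The cost is an edit to the protocol text and a reissued card, with notification to the IRB and FDA. No new procedures or data are needed.
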